1.1.4 Using brain networks to predict tDCS response

Evidence points toward the importance of brain network hubs—nodes that are connected to many other nodes by edges—in neurodegenerative disorders. Nodes with high hub centrality are critical participants in a wide range of network operations supporting cognitive functions (van den Heuvel & Sporns, 2013) and are disproportionately affected in neurological syndromes (Stam, 2014). The tendency for a node to be a hub can be distinguished from more general measures such as network density, the total number of connections in a network, and can be expressed as a hub score, which quantifies the centrality of a node in information processing in a network (van den Heuvel, 2010). Brain regions with especially high hub scores participate in many processing pathways within the brain. Across the spectrum of neurodegenerative disorders, it is suspected that as nodes in critical brain areas are progressively degraded by disease, this is associated with changes in the recruitment of remaining hub nodes (Stam, 2014). Early in the course of degenerative disease, as specific brain regions are selectively affected, it is believed that there is an *increase* in the connectivity of remaining hubs in those regions that partially compensates for lost nodes and helps to maintain performance (Stam, 2014). However, as worsening disease leads to greater node loss, these compensatory changes cannot keep pace with neurodegenerative deterioration, resulting in decreasing hub scores in affected regions (Buckner et al., 2009; Engels et al., 2015). Eventually, when degenerated regions are severely affected, hub scores decline dramatically as the few remaining nodes do not harbor sufficient connections to contribute to networks. In the case of PPA, residual language abilities would then depend on the activity of relatively spared language regions. In a preliminary analysis of 65 subjects with PPA we found that hub scores are indeed decreased in different language centers in PPA variants. Thus, the hub score could serve as a metric in PPA to describe how affected and spared regions impact network functions at different stages of disease. Brain network hubs could also be positively influenced by interventions that enhance their connectivity. We posit that changes in hub scores could also provide a framework for understanding the impact of tDCS on language networks in persons with PPA.

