2.2 Secondary Objectives

- Utilized network analyses to directly interrogate the roles of structural and function connectively in the language network in PPA.
 - Determine whether baseline hub characteristics of the language systems of persons with naPPA/lvPPA, and svPPA influence aphasia severity.
 - Determine whether tDCS induced behavioral effects induce changes in the language network properties.
 - Determine whether structural and functional connectivity features can predict responsiveness to tDCS.

3 Investigational Plan

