8.4.2 Identifying Predictors of Treatment response

We will employ a binary outcome (responder vs. non-responder), based on a change in WAB-AQ of 5 points, which has been recognized as clinically meaningful change in aphasia severity (Elman et al., 1999). We will pursue a series of univariate logistic regression analyses interrogating the following variables, in order to determine which are likely predictors of response to tDCS: PPA variant (naPPA/lvPPA, svPPA, extent of brain atrophy (cortical thickness in the designated language network regions), hub scores, and baseline symptom severity (baseline WAB-AQ). Akaike information criterion (AIC) will be used to develop and select a final model that includes the predictors of tDCS response previously identified as relevant in the univariate analyses. First, the full model containing all relevant predictors will be compared against models with one of each of the predictors removed, to evaluate the extent to which predictors may be correlated or may uniquely contribute to the model despite some potentially shared contribution. The final model will contain age, duration of disease, and sex as covariates and only those predictors identified as unique contributors to tDCS response by the AIC selection procedure.

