8.4.3 Network Neuroscience measures of response to tDCS + CILT

We will first test for the hypothesized relationship between node loss and hub scores by expressing node loss as a quadratic term in a multiple regression using the gray matter thinning at each node in the language network to predict hub scores, covarying for subject age and disease onset, with an FDR-corrected threshold of 0.05. Then, we will use a data-driven machine learning approach—support vector regression—using multivariate hub scores (Fornito et al., 2015) throughout the brain to predict behavior. We will use a leave-one-out cross validation strategy to identify the combination of nonlinearly weighted variables that predict behavior. The value of the machine learning model will be evaluated in terms of percentage of variance explained relative to selecting a similarly sized set of random variables (neuroimaging features including region cortical thickness and individual white matter connections) in 10,000 permutations for both the traditional regression and support vector regression models. It will additionally be tested against network density—the total connectivity of the network—as a control condition. Then, to test whether strong hubs account for the greatest variance in the data, we will correlate the support vector regression weights with region hub scores post-hoc. A significant positive correlation would indicate that stronger hubs account for higher variance in behavioral scores.

We will then use multiple regression to assess stimulation condition as a predictive variable for each language network node. If the predictor illustrates that hub scores increase in the presence of active tDCS, we will test whether effects tend to be concentrated near the site of

CONFIDENTIAL

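### Section 8.4.3 tests whether hub scores predict behaviour better than other imaging features, not whether they predict it at all, so a negative result could not answer the first sub-objective of 2.2

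*Combined protocol and SAP*

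**What the plan says.** The first sub-objective of Section 2.2 is to "Determine whether baseline hub characteristics of the language systems of persons with naPPA/lvPPA, and svPPA influence aphasia severity". The analysis that fits it is in Section 8.4.3: an SVR using hub scores "throughout the brain to predict behavior", with leave-one-out cross-validation ("We will use a leave-one-out cross validation strategy to identify the combination of nonlinearly weighted variables that predict behavior").

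The model's worth is its variance explained "relative to selecting a similarly sized set of random variables (neuroimaging features including region cortical thickness and individual white matter connections". The random sets are drawn "in 10,000 permutations for both the traditional regression and support vector regression models". A second yardstick follows: "It will additionally be tested against network density—the total connectivity of the network—as a control condition".

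For this model the plan gives no permutation of behaviour and no test of variance explained against zero. Later in Section 8.4.3 the pre/post classifiers do get 10,000 null permutations.

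**The concern.** Redrawing the predictors leaves the link between imaging and behaviour intact. The reference distribution shows how well other imaging features of these patients predict behaviour, not how well hub scores would predict it if there were no relation.

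The protocol's own account suggests that the comparators carry disease signal. Section 1.1.4 says that "as nodes in critical brain areas are progressively degraded by disease, this is associated with changes in the recruitment of remaining hub nodes". Section 8.4.3 plans to predict hub scores from gray matter thinning. Section 8.4.2 uses thickness as its atrophy measure: "extent of brain atrophy (cortical thickness in the designated language network regions". If that account is right, thickness and connections should also follow severity. A real hub-severity relation could then fail to stand out from the random sets. At stake is the reading of a negative result for one secondary sub-objective.

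**Working it through.** **Does another analysis fill the gap?**
- Network density (8.4.3) is another imaging measure.
- The FDR-controlled regression (8.4.3) predicts hub scores from thinning. Behaviour is not in it.
- The correlation of SVR weights with hub scores (8.4.3) is post hoc and presupposes a model that predicts.
- The regression on stimulation condition and the pre/post classifiers (8.4.3) concern treatment and change.
- The logistic models (8.4.2) have responder status as outcome.

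None is stated as a test of hub scores against baseline severity.

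**How much could it matter?** The plan gives no power, alpha or effect size for the SVR, so there is no figure to reproduce. The check is a simulation.

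From Section 8.3: 62 enrolled, 31 per variant group, 25% attrition. Sizes used: 62; 62 × 0.75 = 46.5, taken as 46; 31; 31 × 0.75 = 23.25, taken as 23.

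Assumed, not in the documents: 50 hub scores; a pool of 400 other features; 199 draws; 150 replicates per setting; rejection at 0.05; kernel ridge regression with an RBF kernel (penalty 0.3) as a stand-in for SVR.

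Model, with s the latent severity and every e independent standard normal:
- behaviour y = 0.8s + √(1 − 0.8²)e = 0.8s + 0.6e
- each hub score = r_h·s + √(1 − r_h²)e
- each other feature = r_o·s + √(1 − r_o²)e
- leave-one-out R² = 1 − Σ[(yᵢ − ŷᵢ)/(1 − hᵢᵢ)]² / Σ(yᵢ − ȳ)²
- p = (1 + number of draws with R² at or above the observed value)/(199 + 1)

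Test A permutes y across participants. Test B replaces the hubs by 50 features drawn at random from the pool, as the plan does.

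| r_h / r_o | n | A rejects | B rejects | A − B (points) |
|---|---|---|---|---|
| 0.3 / 0 | 62 | 99.3% | 99.3% | 0.0 |
| 0.3 / 0 | 46 | 97.3% | 96.0% | 1.3 |
| 0.3 / 0 | 31 | 92.0% | 88.7% | 3.3 |
| 0.3 / 0 | 23 | 83.3% | 84.0% | −0.7 |
| 0.3 / 0.15 | 62 | 99.3% | 79.3% | 20.0 |
| 0.3 / 0.15 | 46 | 96.7% | 75.3% | 21.4 |
| 0.3 / 0.3 | 62 | 98.0% | 8.0% | 90.0 |
| 0.3 / 0.3 | 46 | 96.0% | 6.7% | 89.3 |
| 0.3 / 0.3 | 31 | 94.0% | 5.3% | 88.7 |
| 0.3 / 0.3 | 23 | 82.0% | 6.0% | 76.0 |
| 0.2 / 0.2 | 62 | 90.0% | 6.7% | 83.3 |
| 0.2 / 0.2 | 46 | 87.3% | 10.0% | 77.3 |
| 0.3 / 0.4 | 62 | 99.3% | 2.7% | 96.6 |
| 0.3 / 0.4 | 46 | 96.7% | 1.3% | 95.4 |
| 0 / 0 | 62 | 4.7% | 7.3% | no relation |
| 0 / 0 | 46 | 4.7% | 6.7% | no relation |
| 0 / 0.3 | 62 | 6.7% | 0.0% | no hub relation |
| 0 / 0.3 | 46 | 4.0% | 0.0% | no hub relation |

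Monte Carlo error is about √(0.8 × 0.2/150) = 0.033, or 3 points, near 80%, and less at the extremes.

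The 0.3 / 0.3 rows follow from the logic. If comparators are as informative as hubs, the hub set behaves like one more random set and reaches the top 5% about 5% of the time at any n. This happens although mean leave-one-out R² is 0.378 at n = 62 and 0.348 at n = 46.

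**What does a failure tell us?** Take n = 62 and r_o = 0.3. Test B fails in 100 − 8.0 = 92.0% of trials when hubs are related to severity and in 100 − 0.0 = 100% when they are not. The ratio is 100/92.0 = 1.09, so a failure is almost no evidence either way.

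**The case against.** The strongest reply is that the benchmark is deliberate. Section 1.1.4 separates hub scores from general measures such as density, and comparison with other imaging features and density tests that specificity. For a claim that hubs matter in particular, it errs on the cautious side. This stands, and it is why the comparisons should be kept.

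Second, Section 8.4.3 does not call the random sets a null and sets no percentile, alpha or decision rule for them. A reader might infer that the plan obliges the sponsor to report a failed test despite a clear hub-severity relation. The text does not say so. The 5% rule in the table is supplied for this check. Leave-one-out variance explained also remains available as a descriptive estimate with a natural zero, though without a significance test.

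Third, the outcome is only called behaviour, so its link to baseline severity is inferred from there being no other candidate analysis. That is a reason to name the score.

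Fourth, the traditional regression in the same sentence is ambiguous. If it is a regression of behaviour on hub scores, an ordinary test against zero might be available. If it is the thinning model, it does not involve behaviour. The plan neither clarifies this nor states such a test.

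**Conclusion.** The point holds for the first sub-objective of Section 2.2. As written, the plan tests relative predictive value. A success would support a hub-severity relation, but a failure could not be interpreted.

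A reader might infer that objective 2.2 as a whole goes unanswered. The documents do not support that. Network change and prediction of response have their own analyses in Sections 8.4.2 and 8.4.3, and even the first sub-objective is answered if hubs beat the benchmark.

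The loss in the chance of detecting a real relation runs from about none (comparators unrelated to severity), through about 20 points (half as strongly linked as hubs), to 76 to 90 points (equally linked) and 95 to 97 points (more strongly linked). The documents do not say where the trial lies. These figures rest on the assumed correlations, feature counts, stand-in learner and rejection rule. The simulation has no variant structure, so permutation within variant group was not itself simulated. The primary WAB-AQ comparison and the safety analysis are unaffected.

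**What to change.** In Section 8.4.3:

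1. Name the behaviour score for this analysis, for example baseline WAB-AQ.
2. Add, as the test for the first sub-objective of Section 2.2, a permutation of that score across participants within PPA variant group. Rerun the full leave-one-out SVR, including any tuning, in each of 10,000 permutations. Permuting within variant keeps a difference between variants in both severity and hub pattern from passing as a hub-severity relation.
3. State what the traditional regression predicts. If it relates hub scores to behaviour, apply the same permutation to it.
4. Keep the random-feature and network-density comparisons as specificity benchmarks, with conclusions limited to whether hub scores predict better than other imaging features.

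The cost is SAP wording and computing time: at most 10,000 × 62 = 620,000 leave-one-out fits for one pooled model without tuning, more if tuning is nested. No new data are needed, and every planned comparison is kept. The change should be made before the analysis, so that the reference distribution is not chosen after the results are seen.

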3.1 General Design

This is a double-blind, sham-controlled, crossover study. Groups will be counterbalanced according to PPA subtype. All participants will undergo baseline language testing and neuroimaging prior to receiving 10 treatment sessions over 2 weeks (Monday-Friday) of either real or sham tDCS paired with mCILT. Immediate post-treatment, 6 week and 12 week follow-ups will be obtained. Participants will then crossover into the second portion of the study whereby they will receive the opposite treatment protocol (real or sham tDCS + mCILT) and an additional 24 week follow-up. Treatment must take place within 2 days to 4 weeks of baseline testing. The overall timeline for each subject's participation is indicated below in Figure 1.

Figure 1: Timeline for each subject

Enrollment	Baseline MRI	Baseline 1	Baseline 2	Treatment	Follow-up	Follow-up MRI	6 week Follow-up	12 week Follow-up	12 week Follow-up MRI	
SCREENING	VISIT 1**	VISIT 2*	VISIT 3*	Visit 4-13	VISIT 14*	VISIT 15**	VISIT 16*	VISIT 17*	VISIT 18**	
- Informed Consent - Screening Forms - Demographics Form	MRI	-CCRSA -WAB 1 -CILT 1 -NWRT -LTROG Oral -PPT Picture -NACC Word Reading -NACC Sentence Repetition	-WAB 2 -CILT 2 -PRT -DDK -LTROG Written -PPT Words -Story -NACC Sentence Reading	tDCS mCILT OR Sham tDCS mCILT	+	- WAB - CILT - NWRT - PRT - LTROG Oral & Written - PPT Picture & Words - NACC Word reading, Sentence Reading & Repetition - DDK - CCRSA - Story	MRI	- WAB - CILT - NWRT - PRT - LTROG Oral & Written - PPT Picture & Words - NACC Word reading, Sentence Reading & Repetition - DDK - CCRSA - Story	-CCRSA -WAB 1 -CILT 1 -NWRT -LTROG Oral -PPT Picture -NACC Word Reading -NACC Sentence Repetition	MRI
~ 1 hour	~ 1 hour	~ 3 hrs	~ 3 hrs	~ 1.5 hrs	~ 3 hrs	~ 1 hour	~ 3 hrs	~ 3 hrs	~ 1 hour	

CONFIDENTIAL

Crossover Baseline	Crossover Treatment	Crossover Follow-up	Crossover Follow-up MRI	Crossover 6 week Follow-up	Crossover 12 week Follow-up	Crossover 12 week Follow-up MRI	Crossover 24 week Follow-up
VISIT 19*	VISIT 20-29	VISIT 30*	VISIT 31**	VISIT 32*	VISIT 33*	VISIT 34**	Visit 35

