3.1.2 Baseline Phase

The baseline phase will consist of 2-3 sessions, each lasting about 2-3 hours depending on the subject's stamina. The purpose of baseline testing is to characterize the subject's language

CONFIDENTIAL

function. To that end, a number of standard language assessments will be administered. These include the Western Aphasia Battery (WAB), Pyramids and Palm Trees (PPT), Philadelphia Repetition Test (PRT), Non-word Repetition Test (NWRT), CILT stimulus naming, Linguistics Test for Reception Of Grammar (LTROG; written & oral), Diadochokinetic (DDK), Spontaneous story telling (Cinderella Story), National Alzheimer's Center Cohort (NAAC) tests, and Communication Confidence Rating Scale for Aphasia (CCRS). Depending on PPA severity, we may have to split these tests over two-three visits instead of one to accommodate for subject fatigue. Additionally, a baseline MRI scan of the brain will be conducted. No contrast will be used.

Baseline visits might be conducted via tele-assessment, using Bluejeans, or a HIPAA compliant alternative. In such cases, testing materials may be mailed to participants beforehand, and instructions provided during the tele-assessment. Other test materials will be displayed over the video software. Video and audio of the tele-assessment will be recorded.

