8.4 Statistical Methods

8.4.1 Treatment Effect on Language Performance

A linear mixed-effects model will be used to determine whether the change in performance induced by tDCS + mCILT for subjects in each PPA variant group differs significantly from that induced by sham stimulation, covarying for age, sex, education and disease duration at time of study if they are imbalanced between the two groups at baseline. The mixed model will include a fixed effect for sequence, period, treatment, and the interaction between treatment and period. A random intercept term will be included in the mixed-effects model to account for correlations from repeated outcome measures. Additional analyses will examine change in other language battery tests, and exploratory analysis will examine baseline aphasia severity as a predictor of response.

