stimulation using a permutation test in which we shuffle the assignment of significant nodes for each network statistic uniformly at random across the brain. If the number of nodes concentrated in the anterior perisylvian nodes encompassed by our area of stimulation is greater than 95% of permutations, it will establish that the effects of mCILT or tDCS + mCILT are local to this region. Moreover, it will allow us to examine whether the effects of stimulation on hub scores are observed in different PPA phenotypes that express pathology at the site of stimulation (as in our nPPA/lvPPA subject) or remote from the site of stimulation (as in our svPPA subjects). Finally, to test if patterns of hub scores across the brain distinguish pre-from post-treatment, we will train support-vector classifiers in a leave-one-out fashion to distinguish pre-and post-treatment conditions within each phenotype using all node hub scores. We will use permutation testing to examine the accuracy of the classifiers against 10,000 null permutations to examine the significance of our results. Further exploratory analyses will examine the specific effect of mCILT alone on language network properties.

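### The node-by-node test of stimulation in section 8.4.3 states no within-person or period term and no multiplicity control, although every participant is scanned under both conditions

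*Combined protocol and SAP*

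**What the plan says.** The design (section 3.1) is a within-person comparison: "This is a double-blind, sham-controlled, crossover study". Section 3.1.2 provides one scan before treatment: "Additionally, a baseline MRI scan of the brain will be conducted". Section 3.1.4 adds scans at the immediate and 12-week follow-ups, and Figure 1 places these in both periods. A participant can therefore have five scans: Visits 1, 15, 18, 31 and 34. Section 6.4.6 makes Visit 18 part of the baseline for the second period.

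Section 8.4.3 contains two node-level regressions.

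- The first predicts hub scores from gray matter thinning, "covarying for subject age and disease onset, with an FDR-corrected threshold of 0.05".
- The second concerns treatment: "We will then use multiple regression to assess stimulation condition as a predictive variable for each language network node". No covariates, repeated-measures term, outcome definition (level or change), time point, significance threshold or multiplicity rule follow it.

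The nodes found significant in the second regression then enter a locality test, which will "shuffle the assignment of significant nodes for each network statistic uniformly at random across the brain". Locality is declared on this condition: "If the number of nodes concentrated in the anterior perisylvian nodes encompassed by our area of stimulation is greater than 95% of permutations".

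For language outcomes, section 8.4.1 handles the same design with a random intercept and a "fixed effect for sequence, period, treatment, and the interaction between treatment and period". Nothing carries that structure over to the imaging analysis.

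**The concern.** Two safeguards that the plan uses elsewhere are absent here. First, real and sham hub scores come from the same brains, in a progressive disease, in two successive periods. A regression that treats scans as independent misstates the standard error of the condition effect, and without a period term, decline over time goes into the residual, or into the condition effect if dropout unbalances the sequences. Second, one test per node with no stated threshold or correction leaves the list of significant nodes without a defined error rate.

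At stake is the secondary objective of showing whether tDCS changes language network properties (section 2.2). The node list is both a result in itself and the input to the locality test.

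**Working it through.** The plan gives no node count, scan correlation, error rate or power for this analysis, so there is no figure of its own to reproduce. The calculations take 25 participants per group and alpha 0.05 (two-sided, assumed) from section 8.3, and the scan schedule from Figure 1. Scan correlations and node counts are assumptions. Scans are taken as equally variable and equally correlated (r) unless stated otherwise.

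**1. One raw scan per condition.** The true variance of the real-minus-sham mean difference is 2σ²(1 − r)/n. An independent-scan analysis uses 2σ²/n. The standard error is therefore overstated by 1/√(1 − r):
- r = 0.5: 1/√0.5 = 1.41
- r = 0.7: 1/√0.3 = 1.83

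Take an effect with 80% power in a paired t-test at n = 25 (0.58 SD of the paired differences). In simulation, the independent-scan test had about 54% power at r = 0.5 and 26% at r = 0.7. Its type I error was about 0.6% and below 0.1%.

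**2. Immediate change.** The two changes are V15 − V1 and V31 − V18, which share no scan. Under equal correlation their covariance is r − r − r + r = 0. Regression on the two changes as if independent is then about correctly sized (about 5% in simulation).

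**3. 12-week change.** The two changes are V18 − V1 and V34 − V18, which share Visit 18.
- Covariance: σ²(r − 1 − r + r) = −σ²(1 − r).
- Variance of each change: 2σ²(1 − r).
- Correlation: −0.5, whatever r is.

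The true variance of the contrast is then 1 + 0.5 = 1.5 times the assumed one. The type I error of a nominal 5% test is 2Φ(−1.96/√1.5) = 2Φ(−1.60) ≈ 11%, and simulation at n = 25 agreed.

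**4. Both follow-up scans of each period as separate rows.** With stronger correlation within a period than between periods, simulated type I error was about 6% to 8% (0.3 between, 0.7 to 0.8 within) and about 11% to 12% (0 between, 0.5 within).

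**5. Multiplicity.** For m independent null nodes, each correctly tested at 0.05, P(at least one false node) = 1 − 0.95^m and the expected number is 0.05m:
- m = 20: 1 − 0.95^20 = 64%; 1.0 expected
- m = 50: 1 − 0.95^50 = 92%; 2.5 expected

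**6. Do steps 1 and 5 hold together?** No. In the conservative case of step 1 at r = 0.5, the per-node error is about 0.64%, so the chance of any false node is 1 − 0.9936^20 = 12% to 1 − 0.9936^50 = 27%. The 64% to 92% applies once each test is correctly sized.

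**The case against.** The strongest reply is that the plan is silent rather than wrong. A multiple regression can carry participant, period and sequence terms or take change scores, and the FDR threshold may have been meant for the whole section. This stands as to wording: the documents do not show that the sponsor chose an uncorrected independent-scan model. But the clause "with an FDR-corrected threshold of 0.05" belongs to the thinning regression, and an analyst following the text would have no instruction to add any of these elements.

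A reader might infer three stronger things that the documents do not support.

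- *That ignoring the correlation always costs power, or always inflates false positives.* Neither holds. The direction depends on whether levels or changes are modelled and on which scans are used, and section 8.4.3 says neither.
- *That false nodes would create a false claim of local effects.* The permutation test takes the number of significant nodes as given. Independent false nodes scattered at random dilute concentration near the electrode rather than produce it. What stands is narrower: the test accepts the list as it is, so it can neither remove false nodes nor restore missed ones.
- *That copying the section 8.4.1 model into the node analysis is enough.* A random intercept cannot represent the negative correlation of the 12-week changes. Its variance would tend to zero and the model would fall back to the independent-scan regression.

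**Conclusion.** The point holds as a gap in specification that has consequences. Followed as written, the node test has a standard error that may be too large, about right or too small, and a node list with no controlled error rate. Under the stated assumptions, power falls from 80% to about 54% to 26% for raw scans, type I error is about 11% for 12-week changes, and uncorrected but correctly sized tests carry a 64% to 92% chance of at least one false node. These figures rest on assumed correlations of 0.5 to 0.7, equal correlation among scans for the change scores, 25 participants, and 20 to 50 independent nodes. Correlated nodes would change the last figure. They describe different scenarios and should not be combined.

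It would be wrong to read this as a threat to the efficacy result: the primary WAB-AQ endpoint has its own mixed model in section 8.4.1. The change should be made, but it concerns a secondary, mechanistic analysis.

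**What to change.** Rewrite the sentence in section 8.4.3 to specify four things.

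1. The outcome and time point: hub score or its change from that period's baseline scan, at the immediate or the 12-week scan.
2. The model: for each node, the participant's real-minus-sham difference regressed on sequence coded +1/−1, with the intercept as the condition effect and the slope absorbing period. Participant fixed effects with period and condition are an equivalent choice for complete pairs. Both are valid whether the within-person correlation is positive or negative. In simulation at n = 25, the difference-on-sequence test kept type I error near 5% for immediate and 12-week changes.
3. The multiplicity rule: the FDR threshold of 0.05 already used in the section, applied across all nodes tested.
4. The order: no node is called significant, or passed to the locality test, before that correction.

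The cost is SAP wording and analysis code, with no new visits or data. The node list will be shorter. Participants without scans in one of the periods add little: at the 25% attrition anticipated in section 8.3, 31 × 0.75 leaves about 23 complete pairs per variant group if every loss removes a pair. If this analysis was always intended, stating it settles the point.
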